Participants will be recruited through social media channels (including online groups), newspaper advertisements, and emails and newsletters from relevant organizations (e.g., the Arthritis Society, Diabetes Canada). After volunteering to participate, participants will set up a phone or video conferencing call with the primary investigator to orient them into the study. Participants will be randomly assigned to either a treatment group or control group. Those assigned to the treatment group will download the mental health chatbot Wysa (Touchkin eServices, Bangalore) on their smartphones. They will be encouraged to interact with the chatbot at least two times per week over a period of four weeks. Participants assigned to the control group will receive no chatbot (i.e., they will be in a no-treatment control group).

Regardless of their group assignment, participants will complete online materials via Qualtrics at the outset of the study, two weeks into the study, and four weeks into the study (i.e., the final assessment point). At the outset of the study, participants will fill out an informed consent form, a demographic questionnaire, and four psychological assessments tools: measures of depression (Patient Health Questionnaire; Kroenke et al., 2001), anxiety (Generalized Anxiety Disorder Scale; Spitzer et al., 2006), stress (Perceived Stress Scale; Cohen & Williamson, 1988), and life satisfaction (Satisfaction with Life Scale; Diener, et al., 1985). Two weeks into the study, participants will complete the four psychological assessment tools a second time. Four weeks into the study, participants will complete the four assessment tools a final time, and those in the treatment group will be presented with a post-study questionnaire that contains qualitative questions regarding their experiences with the chatbot. Participants in both groups will be presented with a debriefing form providing more information about the study. Those in the control group will be given the opportunity to download and use the chatbot.

To facilitate participant compliance, email reminders about outstanding surveys will be sent throughout the week as necessary. In addition, participants in the treatment group will be sent a general reminder about the intervention once per week.

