After the data from the four-week study are analyzed, a subset of participants from the treatment group may be asked to complete optional phone or video interviews to gain more insight into their experiences with and opinions on the chatbot. Approximately 15 to 20 participants will be sought for the interviews. The questions for these interviews will be developed based on the collective results from the quantitative and qualitative analysis described above.

Data Analysis

Quantitative data will be entered into SPSS version 26 (IBM Corp., Armonk, NY, USA) for statistical analysis. Comparisons between the treatment and control groups will be performed using four mixed analysis of variance (ANOVA) statistical tests, with experimental group and health condition as the between-subjects factors, time point as the within-subjects factor, and

mental health outcomes (i.e., scores on the Patient Health Questionnaire, Generalized Anxiety Disorder Scale, Perceived Stress Scale, Satisfaction with Life Scale) as the dependent variables. Significant interactions will be followed up with repeated measures ANOVAs (one within each experimental group) and dependent t-tests with Bonferroni adjustments, as needed.

Qualitative data will be analyzed using Braun and Clarke's (2006) six phases of thematic analysis: (1) familiarize oneself with the data; (2) generate initial codes; (3) search for themes; (4) review themes; (5) define and name themes; and (6) provide the report. This analysis will be performed on the qualitative data from the post-study questionnaire as well as the phone or video interviews. Qualitative data management will be performed with the assistance of NVivo version 12 (QSR International, Burlington, MA, USA).

Implications

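### The Procedure describes assignment and chatbot download before consent and the baseline scales, and nowhere fixes or conceals the order, so baseline scores could depend on a known arm

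*Combined protocol and SAP*

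**What the plan says.** All of this is in the combined protocol and SAP, under Method, Procedure, apart from the analysis model. The steps appear in this order:

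1. Volunteering and a call: "After volunteering to participate, participants will set up a phone or video conferencing call with the primary investigator to orient them into the study". Consent is not mentioned at this step.
2. Assignment, in the very next sentence: "Participants will be randomly assigned to either a treatment group or control group". No time is attached to it.
3. The treatment arm downloads the chatbot. For the other arm: "Participants assigned to the control group will receive no chatbot (i.e., they will be in a no-treatment control group".
4. A new paragraph on assessments, opening with "Regardless of their group assignment, participants will complete online materials via Qualtrics at the outset of the study".
5. The content of that outset session: "At the outset of the study, participants will fill out an informed consent form, a demographic questionnaire, and four psychological assessments tools".

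Under Data Analysis, each of the four scales is analysed by a mixed ANOVA "with experimental group and health condition as the between-subjects factors, time point as the within-subjects factor". The measurements are taken "at the outset of the study, two weeks into the study, and four weeks into the study", so the outset score is one of three levels of time.

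**The concern.** In a randomised comparison, the baseline is useful because nobody's answers to it can depend on the arm. Three features make this design sensitive to losing that protection. The control is no treatment, so participants know their arm as soon as they are told. All four outcomes are self-reported. Baseline is not a covariate but part of the outcome vector, so the treatment claim rests on how the arms differ in their change from it.

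If people learn their arm first, disappointment, hope or a wish to justify the allocation may colour the baseline answers. An arm difference created in that way shows up as differential change even when the chatbot does nothing. Formal consent sits in the same session, so a person who already knows the arm could also decline at that step, before any data exist. Analysis cannot recover such a loss. Entry is exposed only at that step, because volunteering and the call come earlier in the text.

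**Working it through.** **Step 1: does the text fix the order?** Two readings, side by side.

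- *Assignment first.* Call and assignment stand in adjacent sentences: "set up a phone or video conferencing call with the primary investigator to orient them into the study. Participants will be randomly assigned". Download follows, and only then the outset materials, introduced by a clause that takes a group assignment as already existing.
- *Baseline first.* That clause covers all three assessments and may mean only that both arms complete the same scales. The outset of the study can fall before randomisation. The first paragraph also runs ahead to four weeks of chatbot use before the second returns to the outset, so paragraph order is not strict chronology.

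A statement of when randomisation happens, when the arm is disclosed, or who generates and holds the sequence would settle it. None appears under Design, Sample, Setting, Procedure or Data Analysis. Assignment first is thus suggested and permitted, but not proven. Disclosure to a treatment participant can come no later than download, and the text describes download before consent and baseline.

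**Step 2: the plan's own figure.** Inputs from Sample: power .80, alpha .05, correlation .50, required N = 40, target N = 60. The effect is called moderate without a number; I take f = 0.25. For a within-between interaction with k = 4 cells (2 arms × 2 conditions), m = 3 times and sphericity:

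λ = f²·N·m/(1 − ρ) = 0.0625 × 40 × 3 / 0.5 = 15, with df = (k − 1)(m − 1) = 6 and (N − k)(m − 1) = 72.

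Power is 0.805 at N = 40, which reproduces the stated figure, and 0.954 at N = 60. The sample size neither supports nor contradicts this point, and the fix does not change it.

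**Step 3: how a baseline difference reaches the test.** Suppose there is no true effect and the arms differ by d SD at baseline only, so the arm difference over time is (d, 0, 0). Centring over time and splitting equally between the arms gives interaction effects of ±(d/3, −d/6, −d/6). Their squares sum to d²/9 + d²/36 + d²/36 = d²/6, so f² = d²/18.

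λ = N × (d²/6)/(1 − .50), which is 20d² at N = 60 and 13.33d² at N = 40. The arm-by-time test has 2 numerator df and (N − 4) × 2 = 112 or 72 denominator df. Equal allocation is assumed, because the document gives no ratio.

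| Assumed d (SD) | λ, N = 60 | Rejection rate, F(2,112) | λ, N = 40 | Rejection rate, F(2,72) |
|---|---|---|---|---|
| 0 | 0 | 5.0% | 0 | 5.0% |
| 0.1 | 0.20 | 6.5% | 0.13 | 6.0% |
| 0.2 | 0.80 | 11.3% | 0.53 | 9.1% |
| 0.3 | 1.80 | 20.2% | 1.20 | 14.6% |

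The week-4 change contrast is off by the whole shift: 0 − d = −d. Baseline adjustment, which is not planned, would leave half of it: with equal variances the slope is .50, so 0 − .50d = −.50d. A change of model therefore does not replace a change of order.

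**Step 4: direction.** On a symptom scale, a higher baseline in the treatment arm would look like benefit, and a higher baseline among controls would work against the chatbot. On life satisfaction the signs reverse. The documents do not say which, if either, to expect.

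**The case against.** The strongest reply is that the section is organised by topic and that silence on sequence is only silence. That largely stands. A reader might infer that the trial does randomise before consent; the text does not establish this, and baseline first remains compatible with it. Consent pages are also absent from the file, so detail on the consent process may be missing for that reason. What survives is that the baseline-first reading rests on an order the document does not state either, while the order it does describe runs the other way.

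A second reply concerns the figures, and it also stands in part:

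- Every value of d is assumed.
- The calculation supposes that the shift has gone by week 2. A shift persisting equally at all three times would cancel from group by time.
- A shift of (0, d, d), which unmasked reporting could produce after a properly timed baseline, has the same f² = d²/18. The proposed change of order would not remove that.

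The table therefore shows a mechanism and does not estimate the trial's error rate. A reader might be tempted to combine the rates over the four scales into a familywise rate. That would need independent scales with the same shift on each, which the documents do not support, and it would mix in a separate multiplicity question.

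Third, a reader might infer that controls would refuse selectively. That is conjecture: controls are offered the chatbot at the end and completers in either arm a $20 gift card, although the text does not say whether controls know of the later offer in advance. The written order leaves room for selective refusal; nothing shows that it would occur.

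**Conclusion.** The point holds as a defect in the written sequence: the plan describes allocation and download ahead of consent and baseline, states no other order, and describes no concealment. A team could allocate openly before baseline without departing from the document. If it did, and the arm was known, baseline scores and consent could depend on the arm, and any resulting baseline difference would pass into the group-by-time interaction.

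The documents give no size or direction for that bias. The rates of 6.5%, 11.3% and 20.2% are illustrative only. They rest on assumed baseline-only shifts of 0.1, 0.2 and 0.3 SD, 60 participants allocated equally, sphericity, and the plan's correlation of .50. A reader might take them to mean that the planned test has an inflated error rate; the documents support only that the written order allows it. Confidence is medium, and the doubt concerns what the team intends. The change is worth making on either reading: if baseline first was always meant, it documents that; if not, it protects the main comparison.

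**What to change.** Revise the Procedure to state one sequence:

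1. Orientation call.
2. Consent form, demographics and the four baseline scales submitted in Qualtrics.
3. Allocation generated and revealed only after submission, by a mechanism that neither the investigator nor the participant can foresee, for example a randomiser at the end of the baseline survey.
4. Download instructions to the treatment arm.

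Keep the clause about group assignment for the week-2 and week-4 assessments only. Define the randomised set as everyone allocated after completing baseline. If enrolment has already begun, report the order actually used and how many people were assigned but did not go on to consent.

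The cost is a few sentences and a survey-flow setting in software the study already uses, with no extra participants, visits or staff and no change to the sample size. The change secures consent and baseline against knowledge of the arm. It does not address unmasked reporting at weeks 2 and 4.

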Can Mental Health Chatbots Help Chronic Disease Populations?

[Evaluating the Usefulness of an Artificial Intelligence (A.I.) Mental Health Chatbot in a Healthcare Setting]

Protocol and Statistical Analysis Plan

NCT04620668

October 15, 2020

Updated February 13, 2024 for title page, formatting

People dealing with chronic health conditions are susceptible to mental health issues such as depression and anxiety (Clarke & Currie, 2009). Providing conventional mental health services to all of these individuals is not practical given the limited resources of the healthcare system. Artificial intelligence (A.I.) mental health chatbots may be an accessible and costeffective means by which people can receive some degree of mental health support while they cope with their conditions. These automated programs act as a source of virtual support, talking with individuals and providing them with therapeutic exercises to improve their mental wellbeing. Several chatbots have been designed to deliver interventions based on popular psychological therapies (e.g., Wysa, Woebot, and Tess). Research has shown that these programs can reduce symptoms of depression, anxiety, and stress in nonclinical populations (Fitzpatrick et al., 2017; Fulmer et al., 2018; Inkster et al., 2018; Ly et al., 2017). However, the effectiveness of these programs has not been tested in chronic disease populations.

The purpose of the current research is to gain a better understanding of the usefulness of mental health chatbots for chronic disease populations. This research will be guided by two fundamental objectives: (1) to determine whether a mental health chatbot can reduce or prevent negative mental health symptoms in individuals who are dealing with a chronic health condition, and (2) to learn more about how individuals with a chronic health condition view these programs, particularly in terms of their potential benefits or drawbacks when used in healthcare settings. This research will focus on two specific chronic disease populations that are prone to elevated levels of mental health symptoms: people with arthritis and diabetes.

Method

Design

The study objectives will be pursued using a mixed-method research design (Creswell & Plano Clark, 2011), which will involve collecting and analyzing quantitative data on individuals' mental health symptomology and qualitative data on their experiences with the mental health chatbot.

Sample

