Participants will be individuals between the ages of 19 and 65 who have a diagnosis of diabetes (type 1 or type 2 diabetes) or arthritis (osteoarthritis, rheumatoid arthritis, or another type of arthritis). Although people of any age might be susceptible to mental health issues when dealing with these conditions, individuals in the young adult and middle adult age groups may be at particularly high risk because they have to navigate certain life obligations while coping with their conditions (e.g., caring for a young family, working a job) that many older and younger individuals do not. They are also more likely to use and be familiar with chat-based programs than young children or older adults, meaning that they will almost certainly have the modest technical knowledge required to complete the study.

A power analysis conducted using G*Power (Heinrich-Heine-Universität, Düsseldorf) indicated that a total of 40 participants would be required for the quantitative portion of the study, assuming a moderate effect size, .80 power, an alpha level of .05, and a moderate correlation between repeated measures (.50). However, a larger number of participants (N = 60) will be sought to strengthen the analysis. Individuals will be excluded from participation if they are receiving ongoing treatment from a mental health professional, if they already use a mental health chatbot, or if they started or experienced a dosage change in a psychopharmacological drug within the previous month. Participants will also need to have a phone with an active Internet connection. Participants will be offered a \$20 gift card (Canadian funds) to an online retailer of their choice for completing the study. Participants who drop out of the study prior to

completion will be eligible for a \$5 gift card. An additional \$10 gift card will be offered to participants in the treatment group who complete an optional interview following the main study. **Setting**

The study researchers will be based at the Centre for Research in Integrated Care (CRIC) at the University of New Brunswick in Saint John. The centre will provide access to workspace and necessary equipment and software. All participant communication will occur remotely through phone calls, videoconferencing, and/or email. The developer of the chatbot, Touchkin eServices, will provide technical support and assistance to the research team as necessary from their location Bengaluru (Bangalore), India.

Procedure

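### Treatment-arm participants who leave the study or do not answer at week 4 are not scheduled to give their views of the chatbot, so objective 2 is open to selection towards completers

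*Combined protocol and SAP*

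**What the plan says.** The second of the two objectives in the introduction is "to learn more about how individuals with a chronic health condition view these programs, particularly in terms of their potential benefits or drawbacks".

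Two sources serve it.

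- **Week-4 questionnaire (Method, Procedure).** At the final assessment, "those in the treatment group will be presented with a post-study questionnaire that contains qualitative questions regarding their experiences with the chatbot". The mid-point contact carries only the scales: "Two weeks into the study, participants will complete the four psychological assessment tools a second time".
- **Interviews (end of Procedure).** "After the data from the four-week study are analyzed", the plan says, "a subset of participants from the treatment group may be asked to complete optional phone or video interviews". On number: "Approximately 15 to 20 participants will be sought for the interviews". The interview questions are to be developed from the quantitative and qualitative results of the four-week study.

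The Data Analysis section applies thematic analysis to these two sources and to no other.

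Dropout is expected. Under Sample, those who leave before "completion will be eligible for a \$5 gift card", against \$20 for finishing. No dropout rate is stated. The Procedure section also provides email reminders for outstanding surveys.

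**The concern.** Drawbacks are named in the objective itself. The Implications section adds that participants' feedback could help refine these programs and inform policy on their use, including whether to use them at all. Some of the people best placed to describe drawbacks may be those who left because the program did not suit them. The plan foresees leavers but sets no exit questions and no record of why they left.

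The risk is that a drawback known mainly to leavers is under-represented, or does not appear, and that the account of benefits and drawbacks looks more favourable than the experience of the whole treatment arm. This is a separate matter from missing scale scores in the ANOVAs, which concern objective 1.

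**Working it through.** The plan gives no figure on this point, so the check is to go through every contact and ask who is questioned about the chatbot.

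| Contact | Content for the treatment arm | Chatbot views asked? |
|---|---|---|
| Outset | Consent, demographics, four scales | No (not yet used) |
| Week 2 | Four scales | No |
| Week 4 | Four scales and the open-ended questionnaire | Yes |
| Withdrawal | Eligibility for the \$5 card | No |
| After the four-week analysis | Optional interviews with a subset | Yes, if invited and willing |

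The treatment arm can then be split by what happens to each person.

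1. **Uses the chatbot and stays in the study.** Asked at week 4; may be interviewed.
2. **Stops using the chatbot but stays in the study.** Also asked at week 4. Use is encouraged, not required, and the questionnaire goes to the treatment group with no stated condition of use. Reminders apply, and finishing pays \$20 − \$5 = \$15 more than leaving.
3. **Leaves the study before week 4.** No questions are scheduled. An interview is possible but not planned.
4. **Stays silent at week 4 despite reminders.** The questionnaire is missed; an interview is possible but not planned.

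The gap is groups 3 and 4. The interviews do not reliably close it. They are optional, they come late, and no selection rule is given. Their questions are also shaped by the week-4 results, so people who answered at week 4 influence what is asked later.

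**Size, for illustration.** The target of 60 is from the Sample section. The allocation ratio and dropout rate are not stated; 1:1 allocation and 10% to 30% dropout are assumptions.

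- Treatment arm: 60 / 2 = 30.
- 10% dropout: 30 × 0.10 = 3 people without the questionnaire.
- 20% dropout: 30 × 0.20 = 6.
- 30% dropout: 30 × 0.30 = 9.

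These are people not scheduled to be asked. How many would be reached by interview cannot be worked out from the plan.

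**The case against.** The best reply is that the plan already hears from dissatisfied users. Anyone who abandons the chatbot in the first week but remains in the study is sent the questionnaire, is reminded, and has a financial reason to finish. Interviews draw on the treatment group as a whole, not on week-4 completers. People who leave the study may do so for reasons unrelated to the chatbot. No planned analysis becomes invalid.

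Most of this stands, and it rules out three stronger readings that a reader might infer.

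- **That leavers are never asked, so a theme held only by them cannot appear.** The interviews do not bar leavers. The plan is silent on the matter; it does not exclude them.
- **That the analysis hears only from people who put up with the chatbot for four weeks.** Stopping the chatbot and leaving the study are different events, and only the second (or silence at week 4) loses the questionnaire.
- **That the bias can be stated as a percentage.** Suppose a drawback is held by 30% of stayers and 80% of leavers. The whole-arm share would be 0.30 × 0.90 + 0.80 × 0.10 = 35% at 10% dropout, and 0.30 × 0.70 + 0.80 × 0.30 = 45% at 30% dropout, against 30% among stayers. Nothing in the documents supports the 30% or the 80%, and thematic analysis does not estimate prevalence. With 21 to 27 stayers, 30% is still about 6 to 8 people, so that theme would be found.

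The plan also does not say how the \$5 card is delivered, so one cannot assume that the team is in touch with every leaver.

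What the reply does not remove is that those who leave or fall silent have no scheduled route to give their views, and their place in the interviews is left open.

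**Conclusion.** The concern holds in a limited form. Views of the chatbot are scheduled only at week 4, dropout is foreseen, no exit questions exist, and the interview plan does not say whether leavers will be invited. The evidence on drawbacks for objective 2 is therefore open to selection towards study completers.

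The likely direction is towards a more favourable picture, on the assumption that some people leave because of the chatbot. The size is unknown. The range of 3 to 9 people rests on an assumed arm of 30 and an assumed dropout of 10% to 30%, and it counts people outside the scheduled questionnaire, not the distortion of the themes. Objective 2 can still be answered, and the quantitative comparison is unaffected. This is an inexpensive improvement to data collection, not a fault that invalidates the study.

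**What to change.** - **Procedure, week-4 paragraph.** Send the same open-ended questions to any treatment-arm participant who withdraws, or who has not answered the week-4 survey after reminders. State that answering is voluntary and is not a condition of the \$5 card.
- **Procedure, interview paragraph.** State that non-completers are eligible and will be invited within the planned 15 to 20 interviews.
- **Data Analysis.** Add these responses to the thematic analysis. Report how many questionnaire and interview respondents were completers and non-completers, and note any theme raised only by non-completers.

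I would not set a fixed number of interview places for non-completers, nor present two separate sets of themes. With as few as 3 leavers and voluntary response, a separate set could rest on one or two people.

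The cost is one extra survey link, changes of wording and an ethics amendment. The number of interviews and the quantitative analysis do not change. Some leavers will not answer, so the selection shrinks but does not disappear.

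### The three-wave mixed ANOVA by default drops anyone missing a survey, so the arm comparison becomes one of completers; analyse all randomised participants with a mixed model instead

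*Combined protocol and SAP*

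**What the plan says.** All references are to the combined protocol and SAP.

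- **Data Analysis.** "Quantitative data will be entered into SPSS version 26". Treatment and control are compared by "four mixed analysis of variance (ANOVA) statistical tests, with experimental group and health condition as the between-subjects factors, time point as the within-subjects factor", one test per outcome (depression, anxiety, stress, life satisfaction). Then: "Significant interactions will be followed up with repeated measures ANOVAs (one within each experimental group) and dependent t-tests", Bonferroni-adjusted as needed. No analysis set, missing-data method or missing-data sensitivity analysis is named here or elsewhere.
- **Sample.** Finishing earns a $20 "gift card (Canadian funds) to an online retailer of their choice for completing the study". A $5 card is set aside for a second group: "Participants who drop out of the study prior to" completion. No dropout rate is given. The stated requirement is 40 participants; 60 are sought to strengthen the analysis, and this is not described as a dropout allowance.
- **Procedure.** There are three surveys. For both arms, "email reminders about outstanding surveys will be sent throughout the week as necessary". Only one arm uses the chatbot, and "participants in the treatment group will be sent a general reminder about the intervention once per week". Of the controls the plan says that "they will be in a no-treatment control group".

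**The concern.** A mixed ANOVA needs a full set of scores from each person. The repeated-measures procedure normally used for it in SPSS excludes incomplete cases, so someone who misses only week 2 leaves that outcome's test despite having a week-4 score, and someone who leaves after week 2 takes the week-2 score with them.

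The follow-up tests do not repair this. The within-arm ANOVAs drop the same people. The dependent t-tests drop only those missing one of the two scores compared, so successive steps can rest on different participants.

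Randomisation protects the comparison of everyone assigned, not of those who happen to finish. If poorly responding treated participants leave, completers show a false benefit; if worsening controls leave, a false harm. The arms differ in what is asked of them and in how often they are contacted, so different kinds of people could leave each.

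**Working it through.** **1. The plan's own figure.** Taking a moderate effect as f = 0.25 (the number is not given), with correlation .50, 3 waves and 4 cells (2 arms x 2 conditions):

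- noncentrality = f² x N x 3 / (1 - .50) = 0.0625 x 40 x 3 / 0.50 = 15
- df = (4-1)(3-1) = 6 and (40-4)(3-1) = 72; power = 0.805

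So 40 reproduces, as a number of complete cases. At 60 the power is 0.954. Since 60 x 2/3 = 40, one third can be incomplete before the count falls below 40.

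**2. Who is analysed (assumed rates, equal allocation).** If 10% leave before week 2, 10% leave after week 2 and 10% miss only week 2, then 60 - 6 - 6 - 6 = 42 enter the ANOVA (21 per arm), while 42 + 6 = 48 have a week-4 score (24 per arm for a baseline-to-week-4 t-test).

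**3. Bias among completers.** Assume SD 1, all correlations .5, higher = worse, no true effect and no missing week-2 scores. In one arm the chance of missing week 4 is p if a driving score D (SD 1) is above its mean and .05 otherwise; in the other arm it is .10 regardless. Completers in the first arm have mean D shifted by -c, where

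c = √(2/π) x (p - .05) / (2 - p - .05)

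- p = .20: 0.798 x .15/1.75 = 0.068
- p = .30: 0.798 x .25/1.65 = 0.121
- p = .45: 0.798 x .40/1.50 = 0.213

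The bias in mean change from baseline is -c x Cov(change, D):

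| D | Cov, week 2 | Cov, week 4 | Bias in SD at week 2 (p = .20/.30/.45) | Bias in SD at week 4 |
|---|---|---|---|---|
| week-2 change | 1 | .5 | 0.07 / 0.12 / 0.21 | 0.03 / 0.06 / 0.11 |
| week-2 level | .5 | 0 | 0.03 / 0.06 / 0.11 | about 0 |

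Large-sample simulation (4 million) agrees. The bias is a false benefit if this is the treated arm and a false harm if it is the control arm. If dropout is unrelated to D in both arms, each shift is zero whatever the rates. If the same rule holds in both arms, the shifts cancel (simulated -0.003 SD at p = .45).

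The zero at week 4 depends on equal correlations with week 2. With .6 between adjacent waves and .4 from baseline to week 4, the change-driven week-4 bias rises to 0.05 / 0.08 / 0.14 SD.

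**4. False positives.** Group-by-time rejection at nominal 5%, 60 participants, 12,000 simulated trials: change-driven 5.1 / 6.7 / 9.4%; level-driven 5.1 / 5.3 / 6.4%.

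**5. A harsher assumption.** If dropout depends on the baseline score (log-odds slope 1 per SD) in one arm only, at 30% against 10%, the completers' week-4 bias is 0.13 SD. With opposite dependence in the two arms and 30% lost in each, it is 0.25 SD. An estimator using all observed waves gives 0.00 in both.

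**6. The mixed model.** REML, unstructured covariance, 4,000 trials per scenario, fitted with a common baseline mean. Week-4 estimates in the scenarios of step 3 lay within 0.01 SD of zero (change-driven 0.004 / -0.001 / 0.001; level-driven 0.002 / 0.001 / 0.002). Rejection was 5.6 / 6.1 / 5.8% and 6.1 / 5.5 / 6.1%.

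**7. Dropout driven by the unseen week-4 score.** Baseline and week 2 together explain 2(.25)/(1 + .5) = 1/3 of week-4 variance, so to first order 2/3 of c stays in an estimator that uses all observed waves, for either driver below. Completers carry c if dropout follows week-4 change, and c x .5 if it follows week-4 level.

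| Driver | Completers, week 4 | All observed waves, week 4 |
|---|---|---|
| week-4 change | 0.07 / 0.12 / 0.21 SD | 0.05 / 0.08 / 0.14 SD |
| week-4 level | 0.03 / 0.06 / 0.11 SD | 0.05 / 0.08 / 0.14 SD |

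These agree with simulation. In the change-driven row the mixed model rejects 6.5 / 7.0 / 9.8%, against 5.6 / 6.0 / 9.4% for the ANOVA.

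**The case against.** The strongest reply is that the harm is conditional and mostly small, and the remedy imperfect. Much of this stands.

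- **Size.** At p = .45, change-driven, the week-4 bias of 0.105 SD is 0.105/0.284 = 0.37 of the completers' sampling SD. A reader might infer serious inflation of false positives; the main scenarios do not show it. The mixed model itself rejects 5-6%, so its gain is chiefly in bias.
- **Retention.** Completion payment, survey reminders and a four-week follow-up may keep losses low. A reader might infer that the controls, or the treated, will leave selectively and so produce a false benefit. The documents do not show which arm would lose more, or whom.
- **Listwise deletion is not stated.** True. The plan names SPSS but not the procedure, so exclusion is the usual behaviour of the chosen method and not a declared rule.
- **Sample size.** A reader might infer that the trial falls short of its 40. It takes more than one third incomplete. The margin largely protects power but does nothing about bias.
- **The model is no cure.** When dropout follows the unseen week-4 level, it is more biased than the completers' analysis (step 7). This stands and must be disclosed.
- **Power.** A reader might expect recovered scores to raise power much. Assuming effects of 0.25 SD at week 2 and 0.5 SD at week 4, with 20% missing week 4 at random, power is about 31% for the ANOVA on 48 complete cases, 40% for a common-baseline model on the same 48, and 43% with the 12 recovered week-2 scores. Nearly all the gain comes from the baseline constraint, which is a separate matter.

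**Conclusion.** The point holds as a recommended change, not a fatal flaw. The plan foresees incomplete data, does not say how they are handled, and chooses a method that ordinarily discards incomplete participants. When dropout depends on scores already observed, and differently by arm, the completers' comparison is biased while a model using all observed scores is essentially unbiased at week 4.

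Under the step 3 assumptions the week-4 bias runs from about 0 to 0.11 SD, in either direction, with rejection of 5-7% except 9% at the extreme. It reaches 0.25 SD only under harsher assumptions such as opposite selection in the two arms. Every rate is assumed, so these figures show what is possible and do not predict what this trial would see. The stated sample size needs no change.

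**What to change.** In Data Analysis:

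1. Make the primary analysis of each outcome a linear mixed model for repeated measures (SPSS MIXED, REML, unstructured covariance, Satterthwaite degrees of freedom, with heterogeneous compound symmetry as the named fallback) on all randomised participants as assigned. Include group, condition, time and their interactions, with baseline as one of the three outcome waves. Take follow-up contrasts from this model.
2. Report missingness by arm and week. Keep the complete-case mixed ANOVA as a sensitivity analysis.
3. State that the model assumes missing at random, and that it can do worse than completers if dropout follows unseen week-4 levels.
4. Add a brief delta-shift analysis: multiply impute missing scores within arm from condition and observed scores, make dropouts' imputed week-4 scores worse in a few steps (for example 0.1, 0.3 and 0.5 SD; lower for life satisfaction), in each arm in turn, and report where the conclusion changes.

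A common baseline mean across arms is an optional precision gain, separate from missing data.

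**Cost.** SAP wording and somewhat more analysis; no new data. Three shifts x 2 arms x 4 outcomes is 24 sensitivity runs. The model has six covariance parameters and 2 x 2 x 3 = 12 means (10 with a common baseline) per outcome in about 60 people, hence the fallback, and rejects slightly above nominal (5-6% in the simulations with a common baseline).
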